Visit tolerance interval (days)	-8 to -35		±2	±2	±2	±4	±4	±4	±7	±7	±7	±7	±7	±7	±7	±7	±7	±7	±7
Dispense and weigh (tube with cap) TCS ^f	X	X	X	X	X	X	X	X	X	X	X	X	X	X	X	X	X	X	X
Weigh (tube with cap) and record returned TCS ^f		X	X	X	X	X	X	X	X	X	X	X	X	X	X	X	X	X	X
Scales																			
vIGA-AD	X	X	X	X	X	X	X	X	X	X	X	X	X	X	X	X	X	X	X
EASI	X	X	X	X	X	X	X	X	X	X	X	X	X	X	X	X	X	X	X
SCORAD	X	X	X	X	X	X	X	X	X	X	X	X	X	X	X	X	X	X	X
Health Outcomes Measures and Other Questionnaires																			
POEM ^g	X	X	X	X	X	X	X	X	X	X	X	X	X	X	X	X	X	X	X
CDLQI /IDQOL ^g	X	X	X	X	X	X	X	X	X	X	X	X	X	X	X	X	X	X	X
DFI ^g		X	X	X	X	X	X	X	X	X	X	X	X	X	X	X	X	X	X
PROMIS-Depression ^g	X	X		X	X	X	X	X	X	X	X	X	X	X	X	X	X	X	X
PROMIS-Anxiety ^g	X	X		X	X	X	X	X	X	X	X	X	X	X	X	X	X	X	X
EQ-5D-Y ^g		X	X	X	X	X	X	X	X	X	X	X	X	X	X	X	X	X	X
WPAI-AD-CG ^g		X	X	X	X	X	X	X	X	X	X	X	X	X	X	X	X	X	X
Missed School Days for school age children ^g	X	X	X	X	X	X	X	X											
PRISM ^g	X	X	X	X	X	X	X	X											
Itch NRS ^g	X	X	X	X	X	X	X	X											
Skin Pain NRS ^g	X	X	X	X	X	X	X	X											
ADSS ^g	X	X	X	X	X	X	X	X											
PGI-S-AD ^g	X	X	X	X	X	X	X	X											
TCS Use ^g	X	X	X	X	X	X	X	X											

	Screening	Double-blinded Treatment							Long-term Extension Treatment										
	Period 1	Period 3							Period 4										
Visit number	1	2	3	4	5	6	7	8	9	10	11	12	13	14	15	16	17	18	19
Weeks from randomization	0	1	2	4	8	12	16	20	24	28	40	52	64	76	88	100	112	124	
Visit tolerance interval (days)	-8 to -35		±2	±2	±2	±4	±4	±4	±7	±7	±7	±7	±7	±7	±7	±7	±7	±7	±7
C-SSRS and Self-Harm Supplement ^h	X	X	X	X	X	X	X	X	X	X	X	X	X	X	X	X	X	X	X
Self-Harm Follow-up Form ⁱ	X	X	X	X	X	X	X	X	X	X	X	X	X	X	X	X	X	X	X
Laboratory Assessments																			
Clinical chemistry ^{j, q}	X	X			X	X	X	X	X	X	X	X	X	X	X	X	X	X	X
Hematology ^q	X	X			X	X	X	X	X	X	X	X	X	X	X	X	X	X	X
Lipids (fasting) ^{k, q}		X					X			X		X		X		X		X	
IGF-1 and IGFBP-3 ^q		X					X			X		X		X		X		X	
Left hand x-ray ^l (see Section 9.4.9.3 for ongoing patients)		X					X					X		X		X		X	
X-ray of the knee ^l (see Section 9.4.9.3 for ongoing patients)		X							X			X		X		X		X	
Gonadal hormones (patients 8 to <18 years old) ^{m, q}		X					X			X		X		X		X		X	
Serum Pregnancy ⁿ	X																		
TSH	X																		
HIV	X																		
HCV antibody ^o	X																		
HBV testing	X																		
HBV DNAP	X						X			X	X	X	X	X	X	X	X	X	
Urinalysis ^q	X	X			X	X	X	X	X	X	X	X	X	X	X	X	X	X	
Urine Pregnancy ^{n, q}		X		X	X	X	X	X	X	X	X	X	X	X	X	X	X	X	

	Screening	Double-blinded Treatment							Long-term Extension Treatment										
	Period 1	Period 3							Period 4										
Visit number	1	2	3	4	5	6	7	8	9	10	11	12	13	14	15	16	17	18	19
Weeks from randomization	0	1	2	4	8	12	16	20	24	28	40	52	64	76	88	100	112	124	
Visit tolerance interval (days)	-8 to -35		±2	±2	±2	±4	±4	±4	±7	±7	±7	±7	±7	±7	±7	±7	±7	±7	±7
Pharmacogenetics: blood ^q		X																	
Serum IgE ^q		X			X		X			X	X	X	X	X	X	X	X	X	X
Exploratory storage samples (serum and plasma) ^q		X			X		X			X	X	X	X	X	X	X	X	X	X
RNA and biomarkers: blood ^q		X			X		X			X	X	X	X	X	X	X	X	X	X
Baricitinib plasma concentration (PK sample) ^r		X			X	X	X	X											
Antipneumococcal IgG multianalyte Ab assay*																			
Anti-tetanus toxoid IgG, anti-diphtheria toxoid, and anti-pertussis toxoid Ab assay*																			

	Long-term Extension Treatment												PTF/U
	Period 4 – Extended (Patients Randomized to Double-Blind Treatment at Visit 2)												Period 5
Visit number	20	21	22	23	24	25	26	27 ^s	28 ^s	29 ^s	30 ^s	31 ^s / ET ^a	801
Weeks from randomization	136	148	160	172	184	196	208	220	232	244	256	268	
Visit tolerance interval (days)	±7	±7	±7	±7	±7	±7	±7	±7	±7	±7	±7	±7	28 ±4 after last dose
Weight	X	X	X	X	X	X	X	X	X	X	X	X	X
Height ^b	X	X	X	X	X	X	X	X	X	X	X	X	
Vital signs (BP and Pulse) ^b	X	X	X	X	X	X	X	X	X	X	X	X	X
Occipital frontal circumference measurement in patients <3 years old	X	X	X	X	X	X	X	X	X	X	X	X	X
Symptom-directed physical exam ^c	X	X	X	X	X	X	X	X	X	X	X	X	X
Adverse Events	X	X	X	X	X	X	X	X	X	X	X	X	X
Concomitant Medication	X	X	X	X	X	X	X	X	X	X	X	X	X
IWRS	X	X	X	X	X	X	X	X	X	X	X	X	X
IP tablets dispensed (patients ≥10 years old)	X	X	X	X	X	X	X	X	X	X	X		
IP suspension dispensed (patients <10 years old)	X	X	X	X	X	X	X	X	X	X	X		
IP returned and compliance assessed	X	X	X	X	X	X	X	X	X	X	X	X	
Dispense and weigh (tube with cap) TCS ^f	X	X	X	X	X	X	X	X					
Weigh (tube with cap) and record returned TCS ^f	X	X	X	X	X	X	X	X	X			X	X
Scales													
vIGA-AD	X	X	X	X	X	X	X	X	X	X	X	X	X
EASI	X	X	X	X	X	X	X	X	X	X	X	X	X
SCORAD	X	X	X	X	X	X	X	X	X	X	X	X	X

	Long-term Extension Treatment												PTF/U
	Period 4 – Extended (Patients Randomized to Double-Blind Treatment at Visit 2)												Period 5
Visit number	20	21	22	23	24	25	26	27 ^s	28 ^s	29 ^s	30 ^s	31 ^s / ET ^a	801
Weeks from randomization	136	148	160	172	184	196	208	220	232	244	256	268	
Visit tolerance interval (days)	±7	±7	±7	±7	±7	±7	±7	±7	±7	±7	±7	±7	28 ±4 after last dose
Health Outcomes Measures and Other Questionnaires													
POEM ^g	X	X	X	X	X	X	X	X				X	X
CDLQI /IDQOL ^g	X	X	X	X	X	X	X	X				X	X
DFI ^g	X	X	X	X	X	X	X	X				X	X
PROMIS-Depression ^g	X	X	X	X	X	X	X	X				X	
PROMIS-Anxiety ^g	X	X	X	X	X	X	X	X				X	
EQ-5D-Y ^g	X	X	X	X	X	X	X	X				X	X
WPAI-AD-CG ^g	X	X	X	X	X	X	X	X				X	X
C-SSRS and Self-Harm Supplement ^h	X	X	X	X	X	X	X	X	X	X	X	X	X
Self-Harm Follow-up Form ⁱ	X	X	X	X	X	X	X	X	X	X	X	X	X
Laboratory Assessments													
Clinical chemistry ^j	X	X	X	X	X	X	X	X	X	X	X	X	X
Hematology	X	X	X	X	X	X	X	X	X	X	X	X	X
Lipids (fasting) ^k		X		X		X		X		X		X	
IGF-1 and IGFBP-3	X		X		X		X						
Left hand x-ray ^l (see Section 9.4.9.3 for ongoing patients)		X		X		X		X		X		X	
X-ray of the knee ^l (see Section 9.4.9.3 for ongoing patients)		X		X		X		X		X		X	
Gonadal hormones (patients 8 to <18 years old) ^m	X		X		X		X						
HBV DNAP	X	X	X	X	X	X	X	X	X	X	X	X	X
Urinalysis	X	X	X	X	X	X	X	X				X	X

	Long-term Extension Treatment												PTF/U
	Period 4 – Extended (Patients Randomized to Double-Blind Treatment at Visit 2)												Period 5
Visit number	20	21	22	23	24	25	26	27 ^s	28 ^s	29 ^s	30 ^s	31 ^s / ET ^a	801
Weeks from randomization	136	148	160	172	184	196	208	220	232	244	256	268	
Visit tolerance interval (days)	±7	±7	±7	±7	±7	±7	±7	±7	±7	±7	±7	±7	28 ±4 after last dose
Urine Pregnancy ⁿ	X	X	X	X	X	X	X	X	X	X	X	X	X
Serum IgE		X		X		X		X					
Baricitinib plasma concentration (PK sample) ^r												X	
Antipneumococcal IgG multianalyte Ab assay*	At relevant visits for prevaccination, 4 weeks post vaccination, and 12 weeks post vaccination based on the vaccination schedule of each patient. *If patients are eligible for vaccination with tetanus, diphtheria, and pertussis (TDaP) and/or pneumococcal conjugate vaccine according to local recommended schedule of vaccination, IgG titers for eligible vaccine will be evaluated at prevaccination, 4 weeks post vaccination, and 12 weeks post vaccination.												
Anti-tetanus toxoid IgG, anti-diphtheria toxoid, and anti-pertussis toxoid Ab assay*	At relevant visits for prevaccination, 4 weeks post vaccination, and 12 weeks post vaccination based on the vaccination schedule of each patient. *If patients are eligible for vaccination with tetanus, diphtheria, and pertussis (TDaP) and/or pneumococcal conjugate vaccine according to local recommended schedule of vaccination, IgG titers for eligible vaccine will be evaluated at prevaccination, 4 weeks post vaccination, and 12 weeks post vaccination.												

Abbreviations: Ab = antibody; AD = Atopic dermatitis; ADSS = Atopic Dermatitis Sleep Scale; BP = blood pressure; C-SSRS = Columbia Suicide Severity Rating Scale 11 categories suicidal ideation/suicidal behavior; CDLQI = Children’s Dermatology Life Quality Index; DFI = Dermatitis Family Impact; EASI = Eczema Area and Severity Index; ECG = electrocardiogram; eGFR = estimated glomerular filtration rate; EQ-5D-Y = The European Quality of Life-5 Dimensions Youth; ET = early termination; ePRO = electronic patient reported outcomes (device); HBcAb = hepatitis B core antibody; HBV = hepatitis B virus; HCV = hepatitis C virus; IDQOL = Infant’s Dermatitis Quality of Life Index; IgE = immunoglobulin E; IGFBP-3 = insulin-like growth factor binding protein-3; IgG = immunoglobulin G; IP = investigational product; IWRS = interactive web-response system; NRS = numeric rating scale; PGI-S-AD = Patient Global Impression of Severity – Atopic Dermatitis; PK = pharmacokinetics; POEM = Patient Oriented Eczema Measure; PPD = purified protein derivative; PRISM = Parent-Reported Itch Severity Measure; PROMIS = Patient-Reported Outcomes Measurement Information System; PTF/U = post-treatment follow-up; SCORAD = SCORing Atopic Dermatitis; TB = tuberculosis; TCS = topical corticosteroids; TSH = thyroid stimulating hormone; vIGA-AD = validated investigator’s global assessment for atopic dermatitis; WPAI-AD-CG = Work Productivity and Activity Impairment-Atopic Dermatitis-Caregiver.

- a An early termination visit should be conducted if patient discontinues from the study before Visit 31. Visit 801 is the post-treatment follow-up visit, which occurs after the patient has been off IP for approximately 4 weeks. Patients who have permanently discontinued IP but remain in the study for more than 28 days without IP will only complete Visit 31/ET; Visit 801 (follow-up visit) is not required. Patient health outcomes assessments (POEM, CDLQI/IDQOL, DFI, PROMIS-Depression, PROMIS-Anxiety, EQ-5D-Y, WPAI-AD-CG) are collected for the early termination visit but are not collected at Visit 31.
- b Height will be measured using a stadiometer and Sponsor-provided instructions. Blood pressure readings will be collected using the appropriate size pediatric blood pressure cuffs.
- c The symptom-directed physical examination may be repeated at the investigator's discretion any time a patient presents with physical complaints.
- d TB test(s) including PPD, QuantiFERON[®]-TB Gold, and T SPOT[®]. In countries where the QuantiFERON-TB Gold test or T-SPOT is available, either test may be used instead of the PPD TB test. The QuantiFERON-TB Gold test may be performed locally or centrally; the T-SPOT must be performed locally.
- e If PPD testing was chosen to test for TB, then the patient must return and PPD test read 48 to 72 hours after Visit 1 (post-PPD).
- f For patients prescribed sponsor-provided TCS as background treatment. At Visit 28 and beyond, TCS will no longer be provided by the sponsor.
- g The following measures (POEM, CDLQI/IDQOL, DFI, PROMIS-Depression and Anxiety, EQ-5D-Y, and WPAI-AD-CG) should be completed prior to any clinical assessments being performed on days when study visits occur. The following measures are collected via daily diary and should be completed at the end of the patient's day: PGI-S-AD, Itch NRS, Skin Pain NRS, ADSS, PRISM, missed school days, and TCS use.
- h Suicidal ideation and behavior subscales excerpt – Adapted for the assessment of 11 preferred ideation and behavior categories. The C-SSRS will only be collected in patients ≥ 7 years old.
- i The Self-Harm Follow-up Form is only required if triggered by the Self-Harm Supplement Form.
- j Clinical chemistry will include estimated glomerular filtration rate (eGFR, calculated using Bedside Schwartz 2009 formula) calculated by the central laboratory from serum creatinine.
- k Fasting lipid profile: Patients should not eat or drink anything except water for 4 to 12 hours (depending on age and weight as specified in Section 9.4.3) prior to sample collection. If a patient attends these visits in a nonfasting state, this will not be considered to be a protocol violation.
- l Left hand and knee x-rays at an early termination visit is not required if previously taken within 6 months of the early termination visit. The collection of x-rays and other imaging procedures should be discontinued after the patient reaches 18 years of age.
- m Estradiol (for females) or testosterone (for males) will be collected for the assessment of maturation in patients aged 8 to <18 years.
- n Pregnancy tests prior to first dose of investigational product for females ≥ 10 years old of age (<10 years at investigator discretion) if menarche reached or if there is reason to believe the patient is sexually active. Pregnancy test results from Visit 2 must be known prior to first dose of investigational product. A serum pregnancy test (central laboratory) will be performed at Visit 1. Urine pregnancy tests (local laboratory) will be performed at Visit 2 and at all subsequent study visits after Visit 3. If required per local regulations and/or institutional guidelines, pregnancy testing can occur at other times during the study treatment period.
- o For patients who are positive for HCV antibody, a follow-up test for HCV RNA will be performed automatically. Patients who are positive for HCV antibody and negative for HCV RNA may be enrolled.
- p Patients who are positive for hBcAb and negative for HBV DNA may be enrolled. Any enrolled patient who is hBcAb positive, regardless of hBsAb status or level, must undergo HBV DNA testing per the schedule (see Section 9.4.8).

- q At Visit 2 all laboratory samples, with the exception of PK samples, will be obtained prior to the first dose of IP.
- r PK samples will be collected as described in Section 9.5.
- s At Visit 27, patients should be discontinued from study treatment and begin study discontinuation procedures unless sponsor's written approval is obtained to allow the patient to continue on study treatment. Refer to Section 5.1.4.

3. Introduction

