- k Fasting lipid profile: Patients should not eat or drink anything except water for 4 to 12 hours (depending on age and weight as specified in Section 9.4.3) prior to sample collection. If a patient attends these visits in a nonfasting state, this will not be considered to be a protocol violation.
- l Left hand and knee x-rays at an early termination visit is not required if previously taken within 6 months of the early termination visit. The collection of x-rays and other imaging procedures should be discontinued after the patient reaches 18 years of age.
- m Estradiol (for females) or testosterone (for males) will be collected for the assessment of maturation in patients aged 8 to <18 years.
- n Pregnancy tests prior to first dose of investigational product for females ≥ 10 years old of age (<10 years at investigator discretion) if menarche reached or if there is reason to believe the patient is sexually active. Pregnancy test results from Visit 2 must be known prior to first dose of investigational product. A serum pregnancy test (central laboratory) will be performed at Visit 1. Urine pregnancy tests (local laboratory) will be performed at Visit 2 and at all subsequent study visits after Visit 3. If required per local regulations and/or institutional guidelines, pregnancy testing can occur at other times during the study treatment period.
- o For patients who are positive for HCV antibody, a follow-up test for HCV RNA will be performed automatically. Patients who are positive for HCV antibody and negative for HCV RNA may be enrolled.
- p Patients who are positive for hBcAb and negative for HBV DNA may be enrolled. Any enrolled patient who is HBcAb positive, regardless of hBsAb status or level, must undergo HBV DNA testing per the schedule (see Section 9.4.8).
- q At Visit 2 all laboratory samples, with the exception of PK samples, will be obtained prior to the first dose of IP.
- r PK samples will be collected as described in Section 9.5.
- s At Visit 27, patients should be discontinued from study treatment and begin study discontinuation procedures unless sponsor's written approval is obtained to allow the patient to continue on study treatment. Refer to Section 5.1.4.

Table JAIP.2. Schedule of Activities for Patients Randomized to Double-blind Treatment in Study Period 3

	Screening	Double-blinded Treatment							Long-term Extension Treatment										
	Period 1	Period 3							Period 4										

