- TCS and TCNI: Patients who failed systemic therapies intended to treat AD within 6 months preceding screening, such as cyclosporine, methotrexate, azathioprine, systemic corticosteroids, or mycophenolate mofetil will also be considered as a surrogate for having inadequate response to topical therapy.

Intolerance to TCNI is defined as:

- a documented history of clinically significant adverse reactions that in the opinion of the investigator outweigh the benefits of retreatment (e.g., skin burning).

NOTE: if intolerant to TCNI, then the inadequate response criteria above does not need to be met for TCNI but must still be met for TCS.

- [5] Agree to discontinue use of the following excluded medications/treatments for at least 4 weeks prior to Visit 2 and throughout the study unless otherwise specified below:
- a. oral systemic corticosteroids
 - b. systemic immunomodulators, including, but not limited to, cyclosporine, methotrexate, mycophenolate mofetil, and azathioprine
 - c. any other systemic therapy used to treat AD or symptoms of AD (approved or off-label use)
 - d. phototherapy, includes therapeutic phototherapy (psoralen plus ultraviolet-A, ultraviolet-B), excimer laser as well as self-treatment with tanning beds (see Section 7.7.5 regarding use as rescue therapy).
- [6] Agree to discontinue use of the following excluded medications for at least 7 days prior to Visit 2 and throughout the study unless otherwise specified (see Section 7.7):

Patients participating in Study Period 2

- a. TCS or topical immune modulators (e.g., tacrolimus or pimecrolimus)
- b. Topical PDE-4 inhibitor (crisaborole)

Patients participating in Study Period 2 or Study Period 3

- c. Topical JAK inhibitor (e.g., tofacitinib or ruxolitinib) and/or any other investigative topical treatments.

- [7] Have applied emollients daily for at least 14 days prior to Visit 2 and agree to use emollient daily throughout the study.

Patient Characteristics

- [8] Are male or nonpregnant, nonbreastfeeding female patients

Patients of childbearing potential who are abstinent (if this is complete abstinence, as their preferred and usual lifestyle) or in a same-sex relationship (as part of their preferred and usual lifestyle) must agree to either remain abstinent or stay in a same-sex relationship without sexual relationships with the opposite sex.

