Total abstinence is defined as refraining from intercourse during the entirety of the study and for at least 4 weeks following the last dose of IP. Periodic abstinence such as calendar, ovulation, symptothermal, post-ovulation methods and withdrawal are not acceptable methods of contraception.

Otherwise, patients and their partners of childbearing potential must agree to use 2 effective methods of contraception, where at least 1 form is highly effective for the entirety of the study and for at least 4 weeks following the last dose of IP.

The following contraception methods are considered acceptable (the patient and their partner should choose 2, and 1 must be highly effective [defined as less than 1% failure rate per year when used consistently and correctly]):

- Highly effective birth control methods:
 - Combined (estrogen and progestogen containing) hormonal contraception associated with inhibition of ovulation: oral, intravaginal, or transdermal
 - Progestogen-only hormonal contraception associated with inhibition of ovulation: oral, intravaginal or implantable
 - Intrauterine device (IUD)/ intrauterine hormone-releasing system (IUS)
 - Vasectomized partner (with appropriate post-vasectomy documentation of the absence of sperm in the ejaculate).
- Effective birth control methods:
 - Male or female condom with spermicide. It should be noted that the use of male and female condoms as a double barrier method is not considered acceptable due to the high failure rate when these methods are combined.
 - Diaphragm with spermicide
 - Cervical sponge
 - Cervical cap with spermicide
 - Oral contraceptives that do not inhibit ovulation

Note: When local guidelines concerning highly effective or effective methods of birth control differ from the above, the local guidelines must be followed.

Adolescent females who have started menses (even one cycle and any amount of spotting) are considered to be of childbearing potential.

Females of nonchildbearing potential are not required to use birth control and they are defined as:

- Females who are infertile due to surgical sterilization (hysterectomy, bilateral oophorectomy, or tubal ligation), congenital anomaly such as mullerian agenesis, or have not started menses (and are not sexually active)

Informed Consent

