- e For patients <18 years old, eGFR calculated by Bedside Schwartz 2009 formula. For patients ≥18 years old, eGFR calculated using the Chronic Kidney Disease Epidemiology Collaboration [CKD-EPI] Creatinine 2009 equation.
- f Test required at Visit 1 only to determine eligibility of patient for the study.
- g A positive hepatitis C antibody (Hep C antibody) result will be confirmed with an alternate hepatitis C method (HCV RNA).
- h For all females of childbearing potential, a serum pregnancy test will be performed at Visit 1 and a local urine pregnancy test will be performed at Visit 2 and at all subsequent study visits after Visit 3. If required per local regulations and/or institutional guidelines, pregnancy testing can occur at other times during the study treatment period.
- i Gonadal hormones will be collected for patients aged 8 to <18 years.
- j The QuantiFERON®-TB Gold test is the preferred alternative to the PPD test for the evaluation of TB infection. In countries where the QuantiFERON®-TB Gold test or T-SPOT® is available, either test may be used instead of the PPD TB test. The QuantiFERON®-TB Gold test may be performed locally or centrally; the T-SPOT® must be performed locally. If the QuantiFERON®-TB Gold test is indeterminate, 1 retest is allowed. If the retest is indeterminate, then the patient is excluded from the study.
- k HBV DNA testing will be done in those patients who are HBcAb+ at screening.
- l Collection of a sample for bone alkaline phosphatase may be requested by the Sponsor as a reflex test if the alkaline phosphatase result is high.

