12.2. CCI Specific Requirements

This section includes regularly scheduled pregnancy tests for female patients in CCI and to clarify the reassessment of benefit-risk for patients to remain in the trial after Week 16.

Section 2. Schedule of Activities

The following modification has been made to Section 2; see Footnote n.

Table JAIP.2. Schedule of Activities for Patients Randomized to Double-Blind Treatment in Study Period 3

...

	Screening	Double-blinded Treatment							Long-term Extension Treatment										
	Period 1	Period 3							Period 4										
Visit number	1	2	3	4	5	6	7	8	9	10	11	12	13	14	15	16	17	18	19
Weeks from randomization		0	1	2	4	8	12	16	20	24	28	40	52	64	76	88	100	112	124
Visit tolerance interval (days)	-8 to -35		±2	±2	±2	±4	±4	±4	±7	±7	±7	±7	±7	±7	±7	±7	±7	±7	±7
Laboratory Assessments																			
Serum Pregnancy ⁿ	X																		

...

ⁿ Pregnancy tests prior to first dose of investigational product for females ≥10 years old of age (<10 years at investigator discretion) if menarche reached or if there is reason to believe the patient is sexually active. Pregnancy test results from Visit 2 must be known prior to first dose of investigational product. A serum pregnancy test (central laboratory) will be performed at Visit 1. Urine pregnancy tests (local laboratory) will be performed at Visit 2 and at all subsequent study visits after Visit 3. When the interval between scheduled visits exceeds 4 weeks, patients will undergo urine pregnancy self-testing at home approximately every 4 weeks (testing kits to be provided). During these intervisit periods, the site will call the patient approximately every 4 weeks to obtain her pregnancy test results. If required per local regulations and/or institutional guidelines, pregnancy testing can occur at other times during the study treatment period.

Section 5.1.4. Period 4: Long-Term Extension Treatment Period

...

All Patients:

...

The benefit/risk profile will be reassessed throughout the study and patients may be discontinued at any time. In particular, during the long-term extension period, the investigators should continue to assess the benefit/risk profile of patients to remain in the trial after Week 16. For a patient having safety and tolerability issues, or one who is not achieving adequate treatment response, investigators should use clinical judgment on whether to continue or discontinue patient participation in the study.

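### Schedule footnote n leaves pre-dose pregnancy testing of girls under 10 to the investigator even after menarche, while Appendix 2 requires it for all females of childbearing potential

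*Protocol*

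**What the plan says.** Four parts of the Protocol bear on who is tested.

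- **Section 2, Tables JAIP.1 and JAIP.2, footnote n (copied in Appendix 12, section 12.2).** Tests before the first dose are for females aged 10 or over, followed by "<10 years at investigator discretion) if menarche reached or if there is reason to believe the patient is sexually active". The closing bracket in the quotation ends the under-10 exception. The note then requires the Visit 2 result before dosing, places a serum test at Visit 1, and adds: "Urine pregnancy tests (local laboratory) will be performed at Visit 2 and at all subsequent study visits after Visit 3". In 12.2 it also says that, where visits are more than 4 weeks apart, "patients will undergo urine pregnancy self-testing at home approximately every 4 weeks".
- **Appendix 2, footnote h (also copied in 12.2).** "For all females of childbearing potential, a serum pregnancy test will be performed at Visit 1", with local urine tests at Visit 2 and every visit after Visit 3. It gives no age limit and no discretion.
- **Section 6.1, inclusion criterion [8].** Eligible patients "Are male or nonpregnant, nonbreastfeeding female patients". The sentence that defines childbearing potential is: "Adolescent females who have started menses (even one cycle and any amount of spotting) are considered to be of childbearing potential". The nonchildbearing group has two parts. The first is infertility: "infertile due to surgical sterilization (hysterectomy, bilateral oophorectomy, or tubal ligation), congenital anomaly such as mullerian agenesis". The second turns on maturity and is worded "or have not started menses (and are not sexually active". Neither part of that list has an age limit.
- **Section 9.4.3.** The tests detailed in Appendix 2 are to be done as set out in the Schedule of Activities.

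**The concern.** The two notes give different instructions for the same girl. A site working from the schedule could dose a girl under 10 who menstruates on clinical judgement alone. A site working from Appendix 2 would test her first.

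Section 3.3 lists fetal malformation among the important potential risks of baricitinib and cites the exclusion of pregnant patients as one of the protections. A test before dosing is how a site would confirm that exclusion. The schedule makes it optional for girls in whom pregnancy is possible, and at an age where a site might not think of it.

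A second uncertainty follows. The age rule in footnote n is written for tests before the first dose. Its later sentences give type and timing but do not say again who is tested. It is unclear whether the under-10 discretion also applies at later visits and, under 12.2, to the home tests.

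**Working it through.** The check is mainly a comparison of texts; the only arithmetic is a count of scheduled tests.

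**Does the placement of the bracket matter?** The menarche or sexual-activity condition can be read as governing both age groups or only the younger one. On either reading, testing of a girl under 10 with menarche is at discretion.

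**Is she of childbearing potential?** The defining sentence in [8] names adolescent females, which does not clearly cover a 9-year-old. The nonchildbearing list settles it by implication: it admits only infertile females, or those without menses who are also not sexually active. A fertile girl under 10 with menarche or sexual activity is not on that list.

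**Fertile girls under 10, case by case:**

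| Girl under 10 | Footnote n | Footnote h with [8] | Result |
|---|---|---|---|
| Menarche reached | discretionary | required | conflict |
| No menarche, thought sexually active | discretionary | required (by implication of [8]) | conflict |
| No menarche, not sexually active | discretion does no harm | not required | no conflict |

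**Does another section decide?** Section 9.4.3 sends the Appendix 2 tests to the schedule. That can mean the schedule decides who is tested, or only when. On the first reading the weaker rule prevails.

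**Tests within reach of the discretion, per girl.** Inputs are the visit numbers in the two tables and the rule of serum at Visit 1 and urine at Visit 2 and all visits after Visit 3.

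- Table JAIP.2, before the first dose: 1 serum + 1 urine (Visit 2) = 2. This is the express reach.
- Table JAIP.2, through Week 16, if the discretion carries over: 1 serum + 6 urine (Visits 2, 4, 5, 6, 7, 8) = 7.
- Table JAIP.2, full schedule, if it carries over: 1 serum + 1 urine (Visit 2) + 28 urine (Visits 4 to 31) + 1 urine (Visit 801) = 31.
- Table JAIP.1, full schedule, if it carries over: 1 serum + 2 urine (Visits 2 and 4) + 23 urine (Visits 9 to 31) + 1 urine (Visit 801) = 27.

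The home tests in 12.2 are not counted.

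**Number of girls.** Section 5.2 plans at least 120 randomized and at least 10 lead-in patients aged 2 to <10 years, boys and girls together. The Protocol gives no rate of menarche or sexual activity under 10, so no count of affected girls can be derived.

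**The case against.** The case on the other side has five parts.

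1. **The conflict is partly inferred.** Criterion [8] never says expressly that a menstruating 9-year-old is of childbearing potential, and its defining sentence speaks of adolescents. This stands as a limit on the wording. It does not rescue the text: relying on that word would leave the girl in neither group.
2. **Both notes can be obeyed by testing, and other safeguards remain.** The nonpregnant criterion binds everywhere, the Visit 2 result must be known before dosing, local rules may add tests, and Tanner staging and gonadal hormones are scheduled at Visit 2 from age 8. All true. A site that follows footnote n as written may still order no test, and then there is no result to know.
3. **The larger counts depend on a carry-over that the text does not state, and the full-schedule figures are remote.** This stands. Visit 31 is Week 268 in Table JAIP.2, with Visit 801 about 4 weeks after the last dose. At 272/52 ≈ 5.2 years after randomization, a girl still under 10 would have been under about 4.8 years old at entry (10 − 5.2). The figures 31 and 27 are ceilings only.
4. **Discretion in young children is defensible, given blood volumes.** Appendix 13 is aimed mainly at patients 2 to <8 years old and could bear on the serum draw. It gives no reason to make the urine test optional.
5. **The correction leaves [8] alone and states no rule for a girl of 10 or over without menarche or sexual activity.** The correction does not use the term childbearing potential, so it works without changing [8]. Such an older girl is in the nonchildbearing group, and footnote h requires no test of her today either.

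**Conclusion.** The concern holds as a minor safety and eligibility point. Footnote n is less protective than Appendix 2 footnote h for girls under 10 who have reached menarche or are thought to be sexually active, and no other section clearly says which note governs. The express reach is 2 tests per girl. It is 7 through Week 16 in Table JAIP.2 if the discretion carries over, with ceilings of 31 (Table JAIP.2) and 27 (Table JAIP.1) over the full schedules. A girl who turns 10 may leave the discretion, and visits after Visit 27 need sponsor approval.

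The conclusion rests on reading the nonchildbearing list in [8] as complete. The number of girls affected is assumed to be small. No endpoint, analysis or sample size is touched. If all patients have already been dosed, which the Protocol does not say, the pre-dose part is moot, but the question about later visits remains for patients still in the extension.

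**What to change.** In footnote n of Table JAIP.1, of Table JAIP.2 and of the copy in Appendix 12, section 12.2, replace the first sentence with:

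> Pregnancy tests, at the visits below, are required for females of any age who have reached menarche or are thought to be sexually active, unless infertile as defined in inclusion criterion [8]. For females <10 years who have not reached menarche and are not thought to be sexually active, testing is at investigator discretion.

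This keeps discretion only in the harmless case and answers the question about later visits in the same way as footnote h. In the 12.2 copy, the opening phrase should also name the home tests between visits, so that they follow the same rule. Appendix 2 footnote h and criterion [8] can stay as they are.

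The cost is one changed sentence in three places. For the few girls concerned it means one serum test at Visit 1, subject to the Appendix 13 blood-volume guidance, and urine tests already in the schedule (and, under 12.2, the home tests already provided for). No visit or new procedure is added.
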